#### 11.2.1 Response Criteria for AIHA and for CLL

See [Appendix B: AIHA Response Criteria](#) for the definition of clinical response for AIHA.

CLL response will be determined per the investigators' assessment, according to Hallek et al (see [Appendix C: CLL/SLL Response Criteria](#)). Response assessments are to coincide with CT measurements.

#### 11.2.2 CLL Evaluation

Physical examination – physical exams will focus on documenting a change in the number of sites and sizes of lymphadenopathies, hepatomegaly and splenomegaly at the scheduled time points defined above. More extensive physical exams will be performed if guided by the development of new symptoms.

CBC – white blood cell count, hemoglobin and hematocrit, platelet count, and differential count, including both percent and absolute number of lymphocytes. CBC with differential should be assessed at schedule time points defined above.

CT scan of neck, chest, abdomen and pelvis with contrast, will be performed at scheduled time points defined above.

### 11.3 Exploratory Endpoint(s)

Objective	Endpoint	Start	End
Assess the effect of acalabrutinib on T-cell functionality in an autoimmune disorder.	Percentage of T-cell subsets among study participants	Baseline values (prior start of study therapy)	After 3, 6 and 12 cycles

## 12.0 STATISTICAL CONSIDERATIONS

---

### 12.1 Study Design

This is a Phase 2, single-arm, open-label study to assess the efficacy and safety of acalabrutinib in the treatment of CLL patients with AIHA. Refer to [Section 2.4 Overview and Rationale of Study Design](#) for a detailed description of the study design and endpoints.

### 12.2 Sample Size and Power

For warm AIHA, initial treatment with prednisone is associated with responses in 70%-85% of patients; however, even this is short-lived as only 15% to 20% of patients achieve long-term remission upon withdrawal of corticosteroids. Subsequent lines of immunosuppressive therapy (e.g., cyclophosphamide, rituximab) carry initial response rates from 40-60%, but durable responses occur in only 20% to 30% treated patients.

A sample size of 20 achieves an approximate 87% power using a one-sided binomial exact test with a significance level (alpha) of 0.05 for detecting improvement of 0.3 (0.6 from 0.3) in response rate, based upon the assumption that a response of 30% or less indicates no benefit. The actual type I error is 0.048 and the exact binomial test will require 10 or more responders in 20 patients evaluable for the primary endpoint to reject the null hypothesis of 0.3. Anticipating up to 10% patients not evaluable for the primary endpoint, a total of 22 participants will be enrolled.

Study enrollment is anticipated to occur over 36 months at a rate of approximately 7 patients per year

#### 12.2.1 Analysis Populations

The evaluable patients for the clinical endpoints will be eligible participants who received at least 1 dose of protocol treatment, unless otherwise specified in Section 11.1 under the specific/particular endpoint.

The evaluable patients for the exploratory endpoints will be eligible participants who received at least 1 dose of protocol treatment and has at least 1 correlative blood specimen collected on the study.

### 12.3 Study Stopping Rules

The overall study will be paused if any of the following occurs:

- ≥2 of the first six participants develop any grade 4 toxicity (assessed as possibly, probably, or definitely related to study drug) during cycle 1 of treatment, or
- ≥3 of the first 6 participants need to discontinue therapy with acalabrutinib during cycle 1 of treatment due to perceived lack of efficacy, or
- Death with possible or higher attribution to acalabrutinib.

## 12.4 Statistical Analysis Plan

For continuous variables, descriptive statistics will include the mean, standard deviation (or standard error), median, range, and interquartile range. Frequencies and percentages will be displayed for categorical data. Percentages by categories will be based on the number of participants with no missing data (i.e. will add up to 100%). Kaplan-Meier survival curves will be displayed for time-to-event variables. Survival at specific timepoint will be estimated by the Kaplan-Meier product limit estimator along with the Greenwood estimator of standard error; 95% confidence interval will be constructed based on log-log transformation. Median survival time will be estimated when available, along with 2-sided 95% confidence interval (CI) based on Brookmeyer and Crowley method.

### 12.4.1 Analysis of Primary Endpoint

The probability of having AIHA-ORR at 6 cycles will be measured and reported with 95% exact confidence interval (CI). An exact binomial test against a null hypothesis of 30% rate will be performed at the 1-sided alpha of 0.05 to determine whether the AIHA-ORR rate at 6 cycles is disappointing or promising.

### 12.4.2 Analysis of the Secondary Endpoints

The probability of having AIHA-ORR at 3 or 12 cycles will be measured and reported with 95% exact confidence interval. AIHA-specific RFS will be estimated using Kaplan-Meier methods along with 95% confidence interval.

The CLL-ORR after 6 and 12 cycles will be assessed and reported with 95% CI. The Kaplan-Meier method will be used to estimate CLL-specific PFS and DOR, and the summary statistics (e.g., 12-month survival, median survival, 95% confidence intervals) will be provided. DOR will be estimated only among responders (i.e. participants achieving CLL CR/PR at least once).

The frequency of PRBC transfusion will be summarized by descriptive statistics. The difference between the average number of PRBC transfusion per month during protocol treatment vs. the average number of PRBC transfusion at baseline (in the past 6 months before protocol treatment, if available) will be assessed by paired t-test.

Toxicity events will be tabulated and summarized using descriptive statistics such as count and percentages, by severity, attribution, and system organ class according to the CTCAE v5.0 (non-hematologic) and by severity according to IWCLL 2018 (hematologic).

### 12.4.3 Analysis of the Exploratory Endpoint(s)

Flow cytometry will be used to assess T-cell repertoire and evaluate changes associated with acalabrutinib. The distribution of T-cell subtypes distribution will be described by mean, standard deviation (SD), minimal, and maximal values. Comparison of group variables will be assessed using a nonparametric test of independence (e.g., Chi-square test or Fisher's exact test).

## 12.5 Handling of Missing Data

Every attempt will be made to obtain data at the defined time points as described in the primary and secondary endpoints. If the data are not sufficient to analyze specific endpoints, the participant's data may be excluded entirely or partially, depending on the specific endpoints in question. No missing data will be imputed. Whenever possible, all available data will be included in the analysis. A sample size for each analysis will be clearly stated along with the reason for exclusion, if any participant is excluded from the analysis due to missing data.

## **13.0 DATA HANDLING, DATA MANAGEMENT, RECORD KEEPING**

---

### **13.1 Source Documents**

Source documents are original documents, data, and records (e.g., medical records, pharmacy dispensing records, recorded data from automated instruments, laboratory data) that are relevant to the clinical trial. The Investigator or their designee will prepare and maintain adequate and accurate source documents. These documents are designed to record all observations and other pertinent data for each patient enrolled in this clinical trial. Source documents must be adequate to reconstruct all data transcribed onto the case report forms.

### **13.2 Data Capture Methods and Management**

Data for this trial will be collected using City of Hope's electronic capture system (EDC) that is compliant with 21 CFR Part 11.

Study personnel will enter data from source documents corresponding to a subject's visit into the protocol-specific electronic Case Report Form (eCRF).

### **13.3 Case Report Forms/Data Submission Schedule**

The Investigator is responsible for all information collected on subjects enrolled in this study. All data collected during the course of this study must be reviewed and verified for completeness and accuracy by the Investigator. All case report forms must be completed by designated study personnel. The completed case report forms must be reviewed, signed and dated by the Investigator or designee in a timely fashion.

All data will be collected using electronic data collection, stored as indicated in [Section 13.2](#), and will be submitted according to the timelines indicated in [Table 13.3](#).

**Table 13.3 Data Submission Schedule**

Form	Submission Timeline
Eligibility Checklist	Complete prior to registration
On Study Forms	Within 14 calendar days of registration
Baseline Assessment Forms	Within 14 calendar days of registration
Treatment Forms	Within 10 calendar days of treatment administration
Adverse Event Report Forms	Within 10 calendar days of AE assessment/notification
Response Assessment Forms	Within 10 calendar days of the response assessment
Other Assessment Forms (concomitant medications)	Within 10 calendar days of the assessment
Off Treatment/Off Study Forms	Within 10 calendar days of end of treatment/study
Follow up/Survival Forms	Within 14 calendar days of the follow up activity

### **13.4 Regulatory Records**

The Investigator will maintain regulatory records, including updating records in accordance with Good Clinical Practice guidelines and FDA regulations.

## **14.0 REPORTING OF ADVERSE EVENTS, UNANTICIPATED PROBLEMS & OTHER EVENTS OF INTEREST**

---

The research team is responsible for classifying adverse events (AEs) and unanticipated problems (UPs) as defined in the relevant regulations and reporting to all applicable parties, including but not limited to the

COH IRB, DSMC, Food and Drug Administration (FDA), National Institutes of Health (NIH) and other collaborators, e.g., pharmaceutical companies. The research team is responsible for the continued monitoring and tracking of all AEs in order to ensure non-reportable events are reviewed and monitored and do not rise to a reporting level.

#### **14.1 Assessment of Adverse Events**

The site Investigator will be responsible for determining the event name, assessing the severity (i.e., grade), expectedness, and attribution of all adverse events as applicable per the [City of Hope Clinical Research Adverse Event and Unanticipated Problem policy](#) (available from the DCC). Adverse events will be characterized using the descriptions and grading scales found in the most recent version of the NCI CTCAE v5.0. A copy of the scale can be found at:

[https://ctep.cancer.gov/protocoldevelopment/electronic\\_applications/ctc.htm](https://ctep.cancer.gov/protocoldevelopment/electronic_applications/ctc.htm).

The following definitions will be used to determine the causality (attribution) of the event to the study agent or study procedure.

- **Definite** - The event is clearly related to the study treatment, as it follows a reasonable temporal sequence from the time of drug administration and a known response pattern to the study drug, and is not reasonably explained by other factors such as the participant's clinical state, other therapeutic interventions or concomitant drugs administered to the participant.
- **Probable** – The event is most likely related to the study treatment, as it follows a reasonable temporal sequence from the time of drug administration and a known response pattern to the study drug, and is unlikely related to the participant's clinical state, other therapeutic interventions or concomitant drugs.
- **Possible** - The event may be related to study treatment as it follows a reasonable temporal sequence from the time of drug administration, but could have been produced by other factors such as the participant's clinical state, other therapeutic interventions, or concomitant drugs.
- **Unlikely** - The event is unlikely related to the study treatment, and is most likely related to other factors such as the participant's clinical state, other therapeutic interventions, or concomitant medications.
- **Unrelated** - The event is clearly NOT related to the study treatment, and is clearly related to other factors such as the participant's clinical state, other therapeutic interventions, or concomitant medications administered.

#### **14.2 Adverse Events of Special Interest (AESI)**

The following events are adverse events of special interest (AESIs) for participants exposed to acalabrutinib, and must be reported to the sponsor and manufacturer expeditiously, irrespective of regulatory seriousness criteria or causality:

- Ventricular arrhythmias (e.g., ventricular extrasystoles, ventricular tachycardia, ventricular arrhythmia, ventricular fibrillation, etc.)]

##### **14.2.1 Overdose**

On a per dose basis, an overdose is defined as the following amount over the protocol-specified dose of acalabrutinib assigned to a given patient, regardless of any associated adverse events or sequelae.

PO        any amount over the protocol-specified dose

On a schedule or frequency basis, an overdose is defined as anything more frequent than the protocol required schedule or frequency.

Complete data about drug administration, including any overdose, regardless of whether the overdose was accidental or intentional, should be reported.

If the associated AE fulfills serious criteria, Investigators should report the event to the Sponsor within 24 hours using the SAE Reporting Form. The Sponsor should report any SAEs to the IRB and Regulatory Authorities per institutional and/or regulatory guidelines, and to Acerta-Pharma/AstraZeneca per contractual guidelines.

All reports of Overdose should be forwarded to Acerta Pharma/AstraZeneca Data Entry Site (see email address below) within 30 days unless the report meets serious criteria. If report meets serious criteria, it is to be reported to Acerta Pharma/AstraZeneca within 15 calendar days.

#### **14.2.2 Secondary Malignancies**

Adverse Events (AEs) for malignant tumors reported during a study should generally be assessed as Serious AEs. If no other seriousness criteria apply, the 'Important Medical Event' criterion should be used. In certain situations, however, medical judgement on an individual event basis should be applied to clarify that the malignant tumor event should be assessed and reported as a Non-Serious AE. For example, if the tumor is included as medical history and progression occurs during the study, but the progression does not change treatment and/or prognosis of the malignant tumor, the AE may not fulfill the attributes for being assessed as Serious, although reporting of the progression of the malignant tumor as an AE is valid and should occur. Also, some types of malignant tumors, which do not spread remotely after a routine treatment that does not require hospitalization, may be assessed as Non-Serious; examples include Stage 1 basal cell carcinoma and Stage 1A1 cervical cancer removed via cone biopsy. For studies in Early Stage and Late Stage Immuno-Oncology and Oncology Studies: The above instruction applies only when the malignant tumor event in question is a new malignant tumor (i.e., it is not the tumor for which entry into the study is a criterion and that is being treated by the IP under study and is not the development of new or progression of existing metastasis to the tumor under study). Malignant tumors that – as part of normal, if rare, progression – undergo transformation (e.g., Richter's transformation of B cell chronic lymphocytic leukemia into diffuse large B cell lymphoma) should not be considered a new malignant tumor.

### **14.3 Pregnancies**

#### **14.3.1 Female participants:**

Pregnancies and suspected pregnancies (including a positive pregnancy test regardless of age or disease state) of a female participant occurring after the participant receives the first dose of protocol therapy up to 2 days post-last dose of acalabrutinib are considered immediately reportable events. **Protocol therapy is to be discontinued immediately. The pregnancy, suspected pregnancy, or positive pregnancy test must be reported to the Study PI and the DCC immediately within 24 hours of awareness (Section 14.5).** The female subject may be referred to an obstetrician-gynecologist (preferably one with reproductive toxicity experience) or another appropriate healthcare professional for further evaluation.

The Investigator should make every effort to follow the female participant until completion of the pregnancy per institutional policies, and should notify the Study PI.

Abnormal pregnancy outcomes and neonatal deaths that occur within 28 days of birth should be reported as an SAE per expedited reporting guidelines.

Any infant death after 28 days that the Investigator suspects is related to the in utero exposure to protocol therapy should also be reported as an SAE per expedited reporting guidelines. The Study PI or designee will subsequently inform Acerta Pharma/AstraZeneca (Section 14.7)

#### 14.3.2 Male participants:

If a female partner of a male participant becomes pregnant, the male participant should notify the Investigator, and the pregnant female partner should be advised to call their healthcare provider immediately.

The Investigator should make every effort to follow the outcome of the pregnancy per institutional policies, and should notify the Study PI.

### 14.4 Routine AE Collection and Reporting Guidelines

AEs will be collected from the signing of informed consent until ending study participation. Routine AE reporting will occur via data entry into the study eCRF. AEs will be monitored by the Protocol Management Team (PMT). AEs reported through expedited processes (e.g., reported to the IRB, FDA, etc.) must also be reported in routine study data submissions.

Adverse events will be assessed using the [CTCAE v5.0](#) (non-hematologic) and IWCLL 2018 (hematologic). AEs recorded in the eCRF include:

- For Cycle 1, highest grade of each AE type, plus any grade 3 or higher adverse event (regardless of whether or not it is the highest grade);
- For Cycle 2+ through EOT, during each cycle/period, highest grade of each AE type
- All SAEs/AESIs

### 14.5 Expedited Reporting

Table 14.5 indicates what events must be reported expeditiously.

**Table 14.5 Criteria for Expedited Reporting**

Time point	What to report
From signing of the consent to study completion	

• All UPs

For the time period beginning at treatment through 90 days following cessation of treatment, or 30 days following cessation of treatment if the subject initiates new anticancer therapy, whichever is earlier	

• All SAEs regardless of relationship to protocol therapy

• All UPs and AEs that meet the definition of a UP

• AESIs (Section 14.4), overdose

From Day 1 of protocol therapy up to 120 days post-last acalabrutinib dose	

• Pregnancies and lactation

Post Safety Follow-Up to removal from study	

• All SAEs that are considered possibly, probably or definitely related to acalabrutinib.

**NOTE: All events reported expeditiously require follow-up reporting until the event is resolved, stabilized, or determined to be irreversible by the investigator.**

**The DCC should be consulted prior to ending the follow-up of events that have stabilized.**

#### 14.5.1 Expedited reporting guidelines (COH only)

##### 14.5.1.1 *To the DCC/Study PI*

**All events that meet the criteria specified in Table 14.5 will be reported to the DCC and Study PI within 24 hours of notification that the event met the expedited reporting criteria.**

Email the following information to [[contact]](mailto:[contact]) and the Study PI ([contact]): Participant ID, date the event met criteria for reporting, whether the event meets the definition of serious, whether the event is an unanticipated problem, grade of event, attribution of event, whether the event is a known expected toxicity to study agent.

##### 14.5.1.2 *To the COH DSMC/IRB*

Serious Adverse Events that require expedited reporting and unanticipated problems will be reported according to the approved [City of Hope Clinical Research Adverse Event and Unanticipated Problem policy](#). This includes all SAEs and UPs that meet COH DSMC/IRB expedited reporting criteria that occurred at COH and non-COH sites.

##### 14.5.1.3 *To Participating Investigators*

Report all expedited reportable AEs to participating investigators as an IND Safety Report occurring within 30 calendar days of receipt of sponsor (lead site) notification, and indicate whether or not a protocol and/or consent form change is required. A cover letter will indicate the protocol title, the IND#, whether the FDA was informed, and, for non-COH sites, a statement that the report should be submitted to their local IRB for review as an IND safety report if applicable per local IRB policy.

Forward to participating sites all IND safety reports received from Acerta Pharma/AstraZeneca, indicating whether a consent form or protocol change is required within 30 days of notification to Study PI.

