### **2.4 Overview and Rationale of Study Design**

Refer to [Section 12.0 Statistical Considerations](#) for additional information regarding statistical methods used in this study.

This is a single-arm, open label, phase II study to assess the efficacy of acalabrutinib in controlling relapsed or refractory AIHA in a setting of CLL. Participants must meet the inclusion criteria, have none of the exclusion criteria, and have provided written informed consent before the conduct of any screening tests not performed routinely in their treatment.

In this study, eligible participants will have a diagnosis of wAIHA or CAD (cold agglutinin disease) who had a recurrence, did not respond to, or did not tolerate at least one prior AIHA treatment with corticosteroid. Eligible participants will be administered acalabrutinib (100 mg PO BID) daily for 12 cycles (each cycle is 28 days). Treatment with acalabrutinib may be continued beyond 12 cycles if the study participant might benefit from ongoing therapy in the opinion of treating physician (e.g., ongoing therapy for CLL is required); the maximum number of cycles allowed on this study in such situations is 36 cycles. At the end of this treatment period (i.e. after acalabrutinib is discontinued), participants will be considered off-treatment and undergo follow-up evaluations in accordance with institutional standards (refer to [Section10.0 Study Calendar](#)).

A total of 22 participants are planned for enrollment to this study over a period of 36 months. After 6 patients are enrolled on study, investigators will discuss whether it is reasonable to continue accrual based on overall drug safety profile seen in the first 6 patients. Further enrollment will be held if two or more patients (of the first 6 patients) develop any grade 4 toxicity (assessed as possibly, probably, or definitely related to study drug) during cycle 1 of treatment, or if ≥3/6 patients need to discontinue therapy with acalabrutinib during cycle 1 of treatment due to perceived lack of efficacy. Accrual will also be paused any time if any death possibly, probably, or definitely attributed to study treatment occurred.

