#### 14.5.2 Expedited reporting guidelines (non-COH sites only)

##### 14.5.2.1 *To the DCC/Study PI*

**All events that meet the criteria specified in Table 14.5 will be reported to the DCC and Study PI within 24 hours of notification that the event met the expedited reporting criteria.**

1. Non-COH participating sites are to report to their local IRB per their site's specific institutional and IRB guidelines. As soon as possible, non-COH sites will provide to the DCC copies of the IRB submission and corresponding IRB response.
2. Document/describe the AE/UP on each of the following:
  - a. MedWatch 3500A or local IRB submission document\*  
MedWatch 3500A is downloadable form at <http://www.fda.gov/medwatch/getforms.htm>  
\*The local IRB submission document may be used if the document template is approved by the DCC
  - b. Expedited Reporting Coversheet. A modifiable Microsoft Word document is also available from the DCC. An electronic signature on the document will be accepted.
3. Scan and email above documents to the study PI ([[contact]](mailto:[contact])) and [contact] with the subject title as "Acalabrutinib in AIHA SAE COH IRB #20311".
  - a. If available and applicable, sites may include the local IRB submission for this event in the submission.

4. If an email receipt from DCC personnel is not received within one working day, please email [[contact]](mailto:[contact]).

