#### 14.6 Reporting to the FDA

The study PI (or designee) will be responsible for contacting the Office of IND Development and Regulatory Affairs (OIDRA) at COH to ensure prompt reporting of safety reports to the FDA. OIDRA will assist the PI with the preparation of the report and submit the report to the FDA in accordance with the approved [City of Hope's Institutional policy](#).

Serious Adverse Events meeting the requirements for expedited reporting to the Food and Drug Administration (FDA), as defined in [21 CFR 312.32](#), regardless of the site of occurrence, will be reported as an IND safety report using the [MedWatch Form FDA 3500A for Mandatory Reporting](#).

The criteria that require reporting using the MedWatch 3500A are:

- Any unexpected fatal or life threatening adverse experience associated with use of the drug must be reported to the FDA **no later than 7 calendar days** after initial receipt of the information [\[21 CFR 312.32\(c\)\(2\)\]](#)
- Any adverse experience associated with use of the drug that is both serious and unexpected must be submitted **no later than 15 calendar days** after initial receipt of the information [\[21 CFR 312.32\(c\)\(1\)\]](#)
- Any follow-up information to a study report shall be reported **as soon as** the relevant information becomes available. [\[21 CFR 312.32\(d\)\(3\)\]](#)

**In addition**, on behalf of the study PI, OIDRA will submit annually within 60 days (via COH OIDRA) of the anniversary of the date the IND went into effect, an annual report to the FDA which is to include a narrative summary and analysis of the information of all FDA reports within the reporting interval, a summary report adverse drug experiences, and history of actions taken since the last report because of adverse drug experiences.

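### Section 14.5.1.3 allows up to 30 days to tell participating investigators of any expedited safety event, beyond the 7- and 15-day FDA limits, and no time is set for telling sites that a pause rule has been met

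*Combined protocol and SAP*

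**What the plan says.** The protocol sets a separate time limit for each recipient of safety information.

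- **Site to lead site (14.5.1.1 and 14.5.2.1).** For every event that Table 14.5 lists, the rule is that it "will be reported to the DCC and Study PI within 24 hours of notification that the event met the expedited reporting criteria".
- **Lead site to manufacturer (Table 14.6).** Expedited SAE reports are due within 24 hours. The text below the table gives 15 calendar days for SAEs that are not SUSARs.
- **Lead site to FDA (14.6).** The rule for the gravest events begins "Any unexpected fatal or life threatening adverse experience associated with use of the drug must be reported to the FDA", and the limit it sets is "no later than 7 calendar days" from first receipt. Other drug-associated events that are both serious and unexpected are due "no later than 15 calendar days".
- **Lead site to participating investigators (14.5.1.3).** "Report all expedited reportable AEs to participating investigators as an IND Safety Report occurring within 30 calendar days of receipt of sponsor" notification. Manufacturer safety reports are forwarded to sites, with a statement of whether a consent or protocol change is "required within 30 days of notification to Study PI".

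The pause rules appear twice. Section 12.3 says "The overall study will be paused if any of the following occurs", and its list includes a death at least possibly attributed to the drug. Section 2.4 says of such a death: "Accrual will also be paused any time if any death possibly, probably, or definitely attributed to study treatment occurred".

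Section 16.3 makes site investigators members of the PMT and gives the PMT the task of implementing the stopping rules. It recommends that the PMT meet but states no frequency.

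**The concern.** Of the recipients above, the investigators treating exposed participants at other sites have the longest stated limit. Section 14.5.1.3 and Section 14.6 both call the document an IND safety report, yet the deadlines differ, and the 30-day limit makes no distinction by severity. A sponsor could meet every deadline in the protocol while the FDA knows of an unexpected drug-associated death by day 7 and a treating investigator elsewhere learns of it on day 30.

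The notice under 14.5.1.3 also says whether the protocol or consent form must change, and it prompts any local IRB submission. If the notice is late, closer monitoring, updated consent discussions and local IRB review at those sites may be late too.

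The second gap concerns the pause rules. Neither 12.3 nor 2.4 says who tells the sites that a trigger has been met, or how soon.

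**Working it through.** The plan states no figure for this delay, so there is nothing to reproduce. The check compares the stated limits with each other and with the cycle length.

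**Inputs:** 24 hours (14.5.1.1, 14.5.2.1, Table 14.6); 7 and 15 calendar days (14.6); 30 days (14.5.1.3); 28-day cycle (5.2).

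**Step 1: lag behind the FDA limit.** This assumes that both clocks start when the lead site receives the information.

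| Event (unexpected, drug-associated) | FDA limit | Investigator limit | Difference |
|---|---|---|---|
| Fatal or life-threatening | 7 days | 30 days | 30 − 7 = 23 days |
| Other serious | 15 days | 30 days | 30 − 15 = 15 days |

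**Step 2: wait in cycles.** 30 / 28 = 1.07 cycles. Counted from the reporting site's own notification, the limit can reach 1 + 30 = 31 days. If the FDA limits applied to investigators too, the longest wait would be 15 / 28 = 0.54 cycle or 7 / 28 = 0.25 cycle.

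**Step 3: what exceeding one cycle does and does not mean.** A 30-day window always includes the start of a new cycle. It contains a complete day 1 to day 28 cycle for only 3 of the 28 possible starting days.

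**Step 4: which events the comparison covers.** The 30-day rule covers everything in Table 14.5, including SAEs regardless of relationship, overdose and pregnancies. The 7- and 15-day limits cover only unexpected events associated with the drug, so the differences in Step 1 apply to that subset. A related death that is not unexpected can meet a 12.3 trigger with no 7-day FDA clock running. Aligning 14.5.1.3 with 14.6 would therefore not by itself cover every pause trigger.

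**Step 5: how many participants.** At about 7 enrolments a year (12.2) and 12 × 28 = 336 days of treatment, roughly 7 × 336 / 365.25 = 6.4 participants would be on drug at one time across all sites. This assumes that everyone completes exactly 12 cycles; early stopping lowers it, and extension up to 36 cycles raises it. The total includes participants at the lead site and at the reporting site, which already know of the event. The split by site is not given, so the number affected cannot be derived.

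**The case against.** The strongest reply is that the formal safety report is not the only route to the sites. Site investigators belong to the PMT, which implements the stopping rules (16.3), and safety questions raised by the Data and Safety Monitoring Committee go to the same team (16.6). Section 12.3 says the study is paused when a trigger occurs and grants no 30-day grace. Nothing ties the pause to the 14.5.1.3 clock. Central registration and slot control by the DCC (4.2) can stop new enrolment quickly. Some reporting is also governed by institutional policies that are not part of these documents.

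Much of this stands. A reader might infer that the pause rule cannot protect participants at other sites, or that they will take a full further cycle (about 30 × 2 = 60 doses) while their investigators know nothing. The documents do not support that:

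- Thirty days is an outer limit.
- The PMT gives an earlier possible route.
- The dose count would measure a failure of the pause only if the pause were meant to stop dosing. Sections 2.4 and 12.3 do not settle this: one refers to accrual, the other to the study as a whole, and neither mentions participants already on treatment.

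What the reply does not supply is a time limit. PMT meetings are recommended without a frequency, and slot control does not inform anyone treating a participant already on drug. Preparation time does not explain 30 days either, because Table 14.6 expects a completed MedWatch form within 24 hours.

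**Conclusion.** The point holds in limited form. Section 14.5.1.3 sets one 30-day outer limit for all expedited events and for manufacturer safety reports, with nothing shorter for fatal or life-threatening events. For unexpected drug-associated events, that is up to 23 or 15 days after the FDA limit and, at worst, slightly more than one cycle (1.07). Separately, no section of this protocol sets a time for telling sites that a 12.3 trigger has been met.

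The size rests on the worst case the text permits and on both clocks starting at the lead site's receipt. The expected delay and the number of participants affected are unknown. A quicker rule may exist in an institutional policy; only its absence from the protocol is shown. The change is worth making because it is cheap and replaces a stated rule with limits the protocol already uses elsewhere.

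**What to change.** 1. **14.5.1.3, events on this trial.** Require that any event reportable to the FDA under 14.6 reach all participating investigators no later than the same 7- or 15-day limit.
2. **14.5.1.3, manufacturer reports.** Put the forwarding of the manufacturer's IND safety reports on a comparable clock.
3. **12.3.** State that the DCC or PMT notifies all site investigators within a short, stated time when any trigger is met, whether or not the event is also reportable to the FDA. The sponsor should choose the figure; the protocol already works with 24 hours in the opposite direction.
4. **2.4 and 12.3.** Reconcile the two passages on what is paused, and say whether participants already on treatment are affected. This review takes no position on which reading is right.

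The cost is wording in three sections, earlier messages to one or two other sites (the synopsis lists one site besides City of Hope, and Table 9.1.2.3 names a further one), and a slightly tighter DCC workload. The sample size, analysis and trigger thresholds do not change.
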